14.1.4 Sample Size Estimation

Little data exists on the incidence of arrhythmias that occur over an extended period of time following AMI and monitoring strategies for this type of assessment have not been optimized in a clinical trial setting. The primary goal of our study is to characterize the occurrence of arrhythmias in this patient population for 14 days post-AMI and to determine the feasibility of using ambulatory patch ECG monitors to capture this data. These data should be regarded as exploratory with the objective of identifying a meaningful clinical end point that can be easily measured in future, pivotal studies that are adequately powered to detect differences across treatment groups.

Estimating a drop-out rate of approximately 50%, we will need to enroll up to 160 patients in order to obtain a final total sample size of 80 patients. A final sample size of 80 patients will provide 80% power to detect a 37% reduction in INF/VV assuming an SD of 10%, a 24% increase in MSI assuming an SD of 20% and a 39% reduction in Troponin AUC with an SD of 60%. Equal variance was assumed among groups with an unbalanced allocation of patients to placebo (n=20) and combined FDY-5301 treatment groups (n=60).

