7 STUDY DESIGN

This is a Phase 2A, randomized, double-blind, placebo-controlled, multi-center study that will evaluate the safety, efficacy, and PK of FDY-5301 in patients with acute STEMI undergoing PCI.

Patients will receive either FDY-5301 or volume matched placebo after informed consent is obtained and a STEMI diagnosis has been made based on clinical and electrocardiogram (ECG) findings, within an hour prior to myocardial reperfusion.

A minimum of 80 evaluable patients will be enrolled and randomized in a 1:1:1:1 ratio to receive a single dose of 0.5, 1.0, or 2.0 mg/kg FDY-5301 or placebo.

All patients will have an early and late (3 month) cardiac magnetic resonance (CMR) and 14 days of arrhythmia monitoring and will be followed up for safety and efficacy for up to 6 months. Patients will be monitored in hospital, and return for clinic visits 14 days, 30 days, and 3 months post PCI (Figure 1).

Figure 1: Study Diagram

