11.4.2 Secondary Efficacy Analysis

11.4.2.1 Infarct Size Parameters from CMR

INF/VV, MSI, and INF will be assessed by CMR at 72 ± 24 hours post-study drug and 3 months post-study drug. Summary statistics for the observed values along with changes from baseline will be produced for each treatment group and the overall FDY-5301 group for each parameter. The baseline is defined as the measurement taken at the 72 hour timepoint.

For the changes from baseline for each of these parameters, a single pairwise comparison will be performed to analyze the results between all three FDY-5301 groups (overall) and placebo at both the 3 months post-study drug timepoints. An unpaired Student's T-test will be used for the pairwise comparison if the data are normally distributed and a Mann-Whitney rank test will be used for nonparametric data. Normality will be assessed based on the Shapiro-Wilk test at the 5% level. If the unpaired Student's T-test was selected, the difference in means and its 95% confidence interval will be produced.

Each treatment group will also be tested using a one-way analysis of variance (ANOVA) to obtain a common variance followed by a Dunnett's post-test to separately compare each FDY-5301 dose group to placebo.

The same summarization method and statistical analyses will be repeated by baseline TIMI flow (grade 1 and lower, or, grade 2 and 3) and infarct type (anterior or other).

The changes from baseline in infarct size parameters may be compared between treatment groups in the form of a frequency table as necessary. The definition for these changes from baseline categories will be determined at a later stage based on the actual data.

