11.4.2.5 Serum Levels of Troponin

The troponin AUC₀₋₄₈ will be derived from the serum levels of troponin collected at the following timepoints: Predose, 4, 12, 24 and 48 hours post-study drug. AUC₀₋₄₈ will be calculated using the linear trapezoidal method. Where possible, the derivation will be carried out using actual post-dose times recorded. If actual times are missing, nominal times may be used with sponsor approval.

Summary statistics (also including geometric means and geometric coefficient of variation [CV] %) for the serum levels will be produced by each treatment group and the combined FDY-5301 group for the derived AUC₀₋₄₈. The summary statistics for troponin AUC₀₋₄₈ will be presented in a similar way.

The derived AUC₀₋₄₈ will be logarithmically transformed, and an unpaired Student's T-test will be used analyze its differences between all three FDY-5301 groups (overall) and placebo.

The logarithmically transformed AUC₀₋₄₈ from each group will then be tested using a one-way ANOVA to obtain a common variance followed by a Dunnett's post-test to separately compare each FDY-5301 dose group to placebo.

The arithmetic least squares means of the treatment differences will be back-transformed to provide the geometric means and its 95% confidence interval.

The same summarization and statistical analyses will be repeated by baseline TIMI flow (grade 1 and lower, or, grade 2 and 3) and infarct type (anterior or other).

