13 CHANGES FROM THE PROTOCOL SPECIFIED STATISTICAL ANALYSES

For the analysis of arrhythmias of interest, a person-time adjustment will be applied to account for potential missing data during the 14-day monitoring period, due to possible unforeseen reasons such as patient withdrawal, device failure or death. The incidence rate for each treatment group (and overall FDY-5301) will be calculated as the number of events divided by the total person-time of monitoring within each treatment group. The incidence rate ratios of each treatment group (and overall FDY-5301) versus the placebo will be derived.

Scope of the interim analyses has been updated.

Overall summary for primary and exploratory safety and efficacy endpoints will be summarized by stratification of TIMI flow grade and infarct location

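### The overall efficacy comparisons are unadjusted although infarct type and baseline TIMI flow are already used for subgroup repeats; adjusting for them is a cheap gain in precision

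*SAP*

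**What the plan says.** **Overall tests.** SAP 11.4.2.1 (infarct parameters), 11.4.2.4 (cardiac function) and 11.4.2.6 (biomarkers) compare pooled FDY-5301 with placebo by a t-test, or by a Mann-Whitney test if Shapiro-Wilk rejects normality. A one-way ANOVA with Dunnett contrasts for each dose follows. In SAP 11.4.2.5 the troponin AUC is log-transformed and a t-test "will be used analyze its differences between all three FDY-5301 groups (overall) and placebo", followed by the same ANOVA and Dunnett step. Protocol 14.1.6 has the same structure. None of these analyses contains a covariate.

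**Use of the two factors.** In SAP 11.4.2.1 and 11.4.2.4, "The same summarization method and statistical analyses will be repeated by baseline TIMI flow" (grade 0-1 against 2-3) and by infarct type (anterior or other). Sections 11.4.2.5 and 11.4.2.6 say the same in slightly different words. SAP 11.4.1 also uses the factors as strata for arrhythmia summaries and to group Kaplan-Meier curves. SAP 13 lists the change as "Overall summary for primary and exploratory safety and efficacy endpoints will be summarized by stratification of TIMI flow grade and infarct location".

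**Design.** SAP 7 has patients "randomized in a 1:1:1:1 ratio", and Protocol 7.3 refers to a computer-generated code. Neither names infarct type or TIMI flow as a stratification factor.

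**Stated power.** Protocol 14.1.4 says "A final sample size of 80 patients will provide 80% power to detect a 37% reduction in INF/VV assuming an SD of 10" per cent, and "a 39% reduction in Troponin AUC with an SD of 60" per cent, for 20 placebo against 60 pooled active patients.

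**The concern.** By asking for nearly every efficacy analysis to be repeated by infarct type and TIMI flow, the sponsor shows that it expects these factors to matter. Yet the analyses that answer the main question leave them out, and nothing in the documents shows that randomisation balances them. With about 20 evaluable placebo patients, some chance imbalance is to be expected.

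Repeating the tests within subgroups does not help. It produces smaller, separate comparisons and no adjusted overall estimate. Predose troponin is also at hand as a same-analyte baseline for the troponin AUC, but it enters only as the first point of the curve. At stake is precision that needs no further patients, in a trial that expects about 50% dropout and wants to limit the number exposed (SAP 9).

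**Working it through.** **Inputs from the documents.** 20 placebo and 60 active; 80% stated power; troponin reduction 39% with SD 60% (Protocol 14.1.4); log scale for troponin AUC (SAP 11.4.2.5). Alpha and sidedness are not stated; two-sided 5% is taken because 95% intervals are planned.

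**Assumed.** R², the share of outcome variance that the covariates explain. The documents give no figure, so a range from 0 to 0.30 is shown.

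**1. The plan's own figure.** The INF/VV and MSI effects are relative and no placebo mean is given, so their 80% cannot be reproduced. For troponin on the raw scale, d = 39/60 = 0.65. The noncentral t with 78 df gives 80.3% power at one-sided 5% and 70.1% at two-sided 5%. The gain is therefore measured from whichever effect has 80% power unadjusted.

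**2. That effect.** The standard error factor is √(1/20 + 1/60) = 0.258. Power of 80% at two-sided 5% needs d = 0.732.

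**3. With adjustment.** The residual SD becomes SD × √(1 − R²), so d becomes 0.732/√(1 − R²), with 76 df for two covariates. The simulation has 20,000 runs per row and two binary covariates with assumed prevalences of 40% and 70%. It includes chance imbalance and the lost degrees of freedom.

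| R² | adjusted d | power, formula | simulated, unadjusted | simulated, adjusted |
|---|---|---|---|---|
| 0 | 0.732 | 80% | 79.9% | 78.7% |
| 0.05 | 0.751 | 82% | not run | not run |
| 0.10 | 0.772 | 84% | 80.0% | 83.2% |
| 0.20 | 0.819 | 88% | 79.9% | 87.2% |
| 0.30 | 0.875 | 92% | 80.3% | 91.0% |

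The simulated difference goes from −1.2 points at R² = 0 to +3.2 at 0.10. Linear interpolation puts break-even at 0.10 × 1.2/4.4 ≈ 0.03. At R² = 0.20 the gain equals an unadjusted trial of 80/0.80 = 100 patients.

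**4. Troponin as the SAP tests it.** On the log scale the effect is −ln(0.61) = 0.494. There are two ways to carry over the SD of 60%:

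- Log SD 0.6: d = 0.494/0.6 = 0.824, power 88% unadjusted and 91% at R² = 0.10.
- CV 60%: log SD = √ln(1.36) = 0.555, d = 0.891, power 93% unadjusted and 95% at R² = 0.10.

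**5. The subgroup repeats.** For d = 0.732, power is 32% in a subgroup holding 30% of patients (6 against 18), 50% in one holding half (10 against 30), and 65% in one holding 70% (14 against 42). These shares are assumed.

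**The case against.** **The tests are valid and exploratory.** Unadjusted comparisons of randomised groups are valid. Protocol 14.1.6 tests no hypothesis for the primary outcome and calls the secondary efficacy outcomes exploratory. This stands, and it limits the point to efficiency.

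**The tested CMR variable is a change.** A reader might infer that an imbalance in infarct location carries straight into the infarct-size result. SAP 11.4.2.1 and 11.4.2.4 test change from the 72-hour CMR to 3 months, so a factor that moves both scans alike largely cancels. This stands: R² may be small for these variables.

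**Troponin.** A reader might take the 70% in step 1 as the trial's troponin power, or conclude that predose troponin is ignored. The documents support neither. The 70% is raw-scale and two-sided, whereas the SAP tests log AUC, where unadjusted power is 88% to 93%. Predose troponin is used, as the first AUC point.

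**More than 20 placebo patients may contribute.** SAP 11.4 uses the ITT set first. With up to 160 randomised equally to four arms, up to 40 could be placebo patients. At 40 against 120, d = 0.65 has 94% power unadjusted. Unadjusted power would then be higher and the gain in points smaller.

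**Timing of TIMI flow.** Study drug is given up to an hour before reperfusion. The schedule of assessments does not list TIMI flow, and neither document says when it is read relative to the bolus. The general baseline rule in SAP 11.1.1 points to a predose value but does not settle it. This stands and is built into the fix.

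**Conclusion.** The overall comparisons of the continuous efficacy endpoints carry no covariates, and the subgroup repeats do not make up for that. From a base of 80% power with 20 against 60 patients and a two-sided 5% test, adjustment is worth about 2, 4, 8 or 12 points at R² = 0.05, 0.10, 0.20 or 0.30. It costs about one point at R² = 0. For log troponin AUC it is worth about 2 to 3 points at R² = 0.10, from an already high base.

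R² is an assumption throughout, so the documents do not show that the plan loses any particular amount of power. The case rests on asymmetry: the cost is about one point and break-even lies near R² = 0.03. It is stronger for troponin AUC, which is tested directly and has a predose value of the same analyte, than for the CMR changes. It would also be too broad to say that the factors serve only to repeat every test: they define descriptive arrhythmia strata and Kaplan-Meier groups, and the atrial fibrillation analysis in SAP 11.4.3 is not split by them. This is a cheap improvement to an exploratory analysis.

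**What to change.** Before database lock, replace the overall tests in SAP 11.4.2.1, 11.4.2.4, 11.4.2.5 and 11.4.2.6 by one prespecified linear model per endpoint:

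- Terms: treatment (four arms), infarct type (anterior or other) and baseline TIMI flow (0-1 or 2-3). Add log predose troponin for log troponin AUC.
- Include TIMI flow only once it is confirmed as a reading that study drug could not have affected; otherwise use infarct type alone.
- Take the pooled FDY-5301 contrast and the Dunnett dose contrasts from this same model.
- State what replaces the Mann-Whitney route if residuals are not normal, for example a transformation or a rank ANCOVA.
- Keep the repeats by TIMI flow and infarct type as descriptive tables.
- Record the change in SAP 13.

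The cost is SAP wording, a different SAS procedure and two degrees of freedom (three for troponin). No new patients or assessments are needed, apart from confirming when TIMI flow was read.

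### Efficacy tests are repeated within TIMI-flow and infarct-type strata, but the difference in treatment effect between strata is never estimated

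*SAP*

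**What the plan says.** For infarct size (SAP 11.4.2.1), "a single pairwise comparison will be performed to analyze the results between all three FDY-5301 groups (overall) and placebo", by t-test or Mann-Whitney according to a Shapiro-Wilk check, followed by ANOVA and Dunnett comparisons of each dose with placebo. The section then states that "statistical analyses will be repeated by baseline TIMI flow (grade 1 and lower, or, grade 2 and 3) and infarct type (anterior or other"). When the t-test is chosen, "the difference in means and its 95% confidence interval will be produced".

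The other secondary efficacy sections carry a matching sentence, but what it repeats differs:

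- **11.4.2.4 (cardiac function):** the same scheme as 11.4.2.1.
- **11.4.2.5 (troponin AUC):** "The same summarization and statistical analyses will be repeated by baseline TIMI flow" and infarct type. The test is a fixed log-scale t-test plus Dunnett, with no normality switch.
- **11.4.2.6 (biomarkers):** the normality switch for concentrations by timepoint, and log-scale ANOVA and Dunnett for the derived parameters.
- **11.4.2.2 and 11.4.2.3 (ST resolution, persistent arrhythmias):** counts and odds ratios with 95% intervals. No test is named.

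SAP 13 records the addition only as endpoints that "will be summarized by stratification of TIMI flow grade and infarct location". The protocol plans neither subgroup. Neither document contains an interaction term, a between-stratum estimate or a rule for reading stratum results.

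**The concern.** Whether a drug works differently in anterior and other infarcts is a question about the difference between two effects. A p-value in each stratum does not address it, because the strata differ in size and each has far less power than the whole trial. A table with a significant result in one stratum and not in the other is easily read as a finding about who benefits. The protocol presents its arrhythmia data as groundwork for later pivotal studies, so a reader could well use the efficacy tables in the same way.

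The normality switch adds to this. In 11.4.2.1, 11.4.2.4 and the concentration analysis of 11.4.2.6, the check is repeated in each stratum, so the two strata of one factor can be tested by different methods. Where Mann-Whitney is chosen, no interval for the effect is planned.

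**Working it through.** **Inputs.** Protocol 14.1.4 and SAP 9 give 20 placebo and 60 pooled active patients: "A final sample size of 80 patients will provide 80% power to detect a 37% reduction in INF/VV assuming an SD of 10" per cent, "a 24% increase in MSI assuming an SD of 20% and a 39% reduction in Troponin AUC with an SD of 60" per cent. Level and sidedness are not stated; two-sided 5% is assumed, in line with the 95% intervals. Stratum shares are not stated and randomization is not described as stratified; shares from 50/50 to 80/20 are assumed. The true effect is taken to be the same in every stratum.

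**The plan's own figures.** The enrolment target reproduces: 80/(1 - 0.50) = 160. The 80% power cannot be fully reproduced, because placebo means are not given. The standard error of the overall contrast is sqrt(1/20 + 1/60) = 0.258 SD, and 80% power at two-sided 5% needs (1.960 + 0.842) x 0.258 = 0.723 SD (0.732 by noncentral t). That is 7.2 INF/VV points, or 37% only if the placebo mean is about 7.23/0.37 = 19.6%. For troponin, 39/60 = 0.65 SD gives 70% power two-sided and 80% one-sided. Both 0.732 and 0.65 SD are carried forward.

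**One factor, uniform effect.** If the two strata have power a and b, exactly one is significant with probability a(1 - b) + b(1 - a). At 20 versus 60 and 0.732 SD:

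- 50/50: a = b = 0.498, so 2 x 0.498 x 0.502 = 50.0%
- 70/30: 0.644 x 0.682 + 0.318 x 0.356 = 55.3% (rounded inputs give 55.2%)
- 80/20: 0.704 x 0.782 + 0.218 x 0.296 = 61.5%

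The last two columns allow for the ITT analysis if about 40 versus 120 of the 160 randomized contribute; overall power is then 98% at 0.732 SD and 94% at 0.65 SD.

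| Share | 20 v 60, 0.732 SD | 20 v 60, 0.65 SD | 40 v 120, 0.732 SD | 40 v 120, 0.65 SD |
|---|---|---|---|---|
| 50/50 | 50.0% | 48.4% | 32.1% | 41.9% |
| 70/30 | 55.3% | 52.1% | 43.8% | 51.4% |
| 80/20 | 61.5% | 56.5% | 57.9% | 62.5% |

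**Both factors.** Simulation (40,000 trials per setting, two independent factors, 20 versus 60, 80% overall power) gives at least one discordant factor in 68% (both 50/50), 72% (70/30 with 50/50 or 40/60) and 76% (80/20 with 40/60).

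**No effect.** The two strata of one factor give 1 - 0.95^2 = 9.75%. Four independent tests would give 1 - 0.95^4 = 18.5%; the two factors share patients, and simulation gives about 16% per outcome.

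**What the missing estimate would show.** Under a uniform effect an interaction test rejects in about 5% of trials. Among trials with exactly one significant stratum, only 6-9% have interaction p<0.05.

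**Precision of that estimate.** With share f, its standard error is 0.258/sqrt(f(1 - f)). The 95% half-width is 1.96 x 0.516 = 1.01 SD at 50/50, 1.96 x 0.563 = 1.10 at 70/30 and 1.96 x 0.596 = 1.17 at 75/25.

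**Volume.** Eight continuous outcomes (INF/VV, MSI, INF, EDV, ESV, FS, EF, troponin AUC) x 4 comparisons x 4 strata x 2 populations (ITT and PP, SAP 11.4) = 256 stratum comparisons, before biomarkers.

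**The case against.** The strongest reply is that these outcomes are labelled exploratory, that SAP 13 speaks only of summaries by stratum, and that intervals already accompany the stratum odds ratios, the t-test differences and the geometric means. A careful reader could compare strata informally. That stands and limits the harm. It does not supply the between-stratum difference, and sections 11.4.2.1 and 11.4.2.4 to 11.4.2.6 repeat tests, not only summaries.

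The 80% premise is also borrowed. The tests in 11.4.2.1 and 11.4.2.4 are on change from the 72-hour scan to 3 months, for which neither document states an effect or SD. The figures are illustrative there; troponin AUC is the closest match. The ITT set may exceed 80 patients, which lowers discordance at equal splits.

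An interaction estimate will be imprecise. At equal strata, power to detect an interaction as large as the main effect is about 29%. This is a reason to report an interval and not a test alone. It does not make the stratum p-values more informative.

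**Conclusion.** The gap is real and of moderate weight: tests are repeated within strata and the quantity that would show a subgroup difference is not produced. Under the stated assumptions, a uniform effect gives exactly one significant stratum in about 50-62% of trials per factor at 20 versus 60 and 80% power (48-57% at the 0.65 SD troponin effect; about 32-63% at about 40 versus 120). At least one of the two factors is discordant in about 70%. All of this rests on assumed stratum shares.

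Three stronger readings are tempting and not supported:

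- **That a uniform effect will usually look confined to one subgroup.** For a single factor and outcome it is about an even chance at an equal split. It is clearly more likely than not only for unequal splits or across both factors.
- **That every efficacy analysis repeats a full set of tests in each stratum.** Sections 11.4.2.2 and 11.4.2.3 have odds ratios only, and 11.4.2.5 has no normality switch.
- **That the plan intends to select a target population from stratum results.** No text says so; that misuse is a prediction about readers.

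No primary conclusion depends on this point.

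**What to change.** Before database lock, amend the SAP as follows.

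- **11.4.2.1 and 11.4.2.4 to 11.4.2.6:** for each continuous outcome and subgroup factor, fit one linear model with treatment (overall FDY-5301 versus placebo), subgroup and their interaction, on the log scale for troponin AUC and the other log-transformed parameters. Report the effect in each stratum and the between-stratum difference, each with a 95% interval, in place of the within-stratum t, Mann-Whitney and Dunnett tests.
- **11.4.2.2 and 11.4.2.3:** keep the stratum odds ratios with intervals. Where counts allow, add the ratio of odds ratios for overall FDY-5301 versus placebo with its interval. Section 11.4.2.3 currently gives odds ratios by dose group only, so the overall odds ratio must be added there.
- **Interpretation:** state that a subgroup difference is judged only from the between-stratum estimate, not from one stratum being significant and the other not.

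The cost is SAP wording and fewer tables. The downside is that the interval for the difference will be wide, about +/-1.0 SD at equal strata and 1.1-1.2 SD at a 70-75% split. That is an honest statement of what a trial of this size can say about subgroups.

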11.4.2.2 Proportion of Patients with ST-segment Resolution at 4 hours Post-study Drug

12-lead ECGs will be used to obtain baseline ST-segment elevation prior to treatment in order to evaluate ST-segment resolution 4 hours post-study drug.

ST-segment resolution will be defined as a reduction of the ST-segment elevation by 50% when compared to the baseline. Evaluation of the percentage of ST-segment resolution will be undertaken on the single worst ECG lead (defined as the lead with the maximal ST-segment elevation). Baseline is defined as the maximal ST-segment elevation obtained at Day 1 screening. Results will be categorized as either resolved or non-resolved.

The number of patients with ST-segment resolution will be tabulated by treatment group. Odds ratios will be calculated for each FDY-5301 treatment group (and overall) against the placebo group, along with its 95% confidence interval.

The same summarization method and statistical analyses will be repeated by baseline TIMI flow (grade 1 and lower, or, grade 2 and 3) and infarct type (anterior or other).

Clinician's ECG interpretation collected from the eCRFs will be listed.

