14.1.3 Study Outcomes

The primary outcome for this study will be the combined number and incidence rate of several arrhythmias of interest that occur in each group over a 14 day period post-study drug. These arrhythmias including ventricular fibrillation, sustained ventricular tachycardia (≥ 125 BPM, ≥ 30 seconds), non-sustained ventricular tachycardia (≥ 125 BPM, ≥ 16 beats, < 30 seconds) and high degree AV block (2nd or 3rd degree, ≥ 8 beats) were chosen because they are significant

prognostic indicators of depressed left ventricular ejection fraction and cardiac death [1]. The combined number of arrhythmic events in each group will be calculated along with the arrhythmia incidence rate defined as the percentage of patients in each group experiencing at least one of the defined arrhythmias of interest.

An exploratory sub-analysis will be conducted to determine the number and incidence rate of each separate arrhythmia type per dose group.

Secondary exploratory efficacy outcomes will include:

Infarct size as a proportion of ventricular volume (INF/VV), the myocardial salvage index (MSI), absolute MI size (INF) at 72 +/- 24 hours and 3 months post study drug measured by CMR.

The proportion of patients with ST-segment resolution at 4 hours post study drug.

Serum levels of troponin calculated as AUC 0-48 hours post study drug.

Cardiac-related adverse events including the development of heart failure.

The incidence of all-cause and cardiac mortality out to 6 months post PCI.

In addition to the measurement of safety and efficacy parameters in this study, serum biomarker levels of cardiac injury, inflammation and remodeling will also be assessed.

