14.1.6 General Analysis of Safety and Efficacy Outcomes

Analysis of the primary safety outcome: characterize the number and incidence rate of serious arrhythmias that occur during a 14-day interval in this patient population. No hypothesis will be tested and data will be descriptive in nature only. A more detailed analysis strategy will be outlined in the SAP.

Analysis of exploratory secondary efficacy outcomes: For all variables with a continuous outcome including infarct size relative to the VV, MSI, absolute MI size, cardiac function, biomarkers of cardiac injury and cardiac troponin levels, a single pairwise comparison to analyze differences between all three FDY-5301 groups (combined) and placebo will be used. An unpaired Student's T test will be used for the pairwise comparison if the data are normally distributed and a Mann-Whitney rank test will be used for nonparametric data. Each group will then be tested using a one-way analysis of variance (ANOVA) to obtain a common variance followed by a Dunnett's post-test to separately compare each FDY-5301 dose group to placebo.

For categorical outcome including ST-segment resolution and incidence of all-cause and cardiac related mortality or morbidity, odds ratios comparing each FDY-5301 treatment group with placebo will be calculated.

Physical examination data from baseline, post-study and **medical history** data at baseline and peri-procedural arrhythmia data will be listed by patient. All clinical safety and tolerability data will be listed for each subject. **Laboratory values** will be calculated as group mean data and presented in shift tables. Comments as to the clinical significance of out of range values will be listed separately. **Adverse event** data will be summarized by group, visit, severity, and possible relationship to the study drug.

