9 SAMPLE SIZE JUSTIFICATION

As this is the first clinical study of FDY-5301 in patients, safety is the primary focus. For this reason, the goal is to expose a limited number of patients to FDY-5301 while still powering the study to detect significant differences in efficacy measures across groups. A total sample size of 80 patients will provide 80% power to detect a 37% reduction in infarct size (INF) / ventricular volume (VV) assuming a standard deviation (SD) of 10%, a 24% increase in MSI assuming a SD of 20% and a 39% reduction in Troponin area under the curve (AUC) with an SD of 60%. Equal variance was assumed among groups with an unbalanced allocation of patients to placebo (n = 20) and overall FDY-5301 treatment groups (n = 60).

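### Percentage ST resolution at 4 hours is evaluated for each patient but compared only after a cut at 50%; a supportive comparison of the percentage itself would be more precise at almost no cost

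*SAP*

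**What the plan says.** SAP section 11.4.2.2 starts from a measured quantity: "Evaluation of the percentage of ST-segment resolution will be undertaken on the single worst ECG lead". It then sets the cut: "ST-segment resolution will be defined as a reduction of the ST-segment elevation by 50% when compared to the baseline". After that, "Results will be categorized as either resolved or non-resolved". The analysis is a table of counts plus odds ratios: "Odds ratios will be calculated for each FDY-5301 treatment group (and overall) against the placebo group, along with its 95% confidence interval". The same analysis is repeated by baseline TIMI flow and infarct type. No summary or comparison of the percentage is planned.

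Protocol section 14.1.6 lists ST resolution among the categorical outcomes, for which "odds ratios comparing each FDY-5301 treatment group with placebo will be calculated". Protocol section 14.1.3 places it under the wording "Secondary exploratory efficacy outcomes will include" and defines it as a proportion of patients.

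The other outcomes measured on a continuous scale are compared as such. Infarct size (SAP 11.4.2.1), cardiac function (11.4.2.4), troponin AUC (11.4.2.5) and biomarkers (11.4.2.6) each get a t test, with Mann-Whitney as the alternative except for troponin AUC, and then ANOVA with Dunnett.

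**The concern.** After the cut, 51% and 100% resolution count the same, and 49% counts as failure. ST resolution is the only efficacy outcome in the SAP that is evaluated as a percentage and then split in two before any comparison. In a small trial this makes the treatment contrast less precise than the data allow. Protocol section 14.1.4 says the trial should help identify an endpoint for later pivotal studies. The size and spread of the effect on ST resolution would be useful for that, and a yes/no table does not show them.

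**Working it through.** **The plan's own figure.** There is none for ST resolution. The 80% power in SAP section 9 covers INF/VV, MSI and troponin AUC only. Troponin is the only one whose standardised effect can be read directly: 39/60 = 0.65. At 20 versus 60 that gives about 80% power at one-sided 0.05 and about 70% at two-sided 0.05. Sidedness is not stated, which is a separate matter. The figure serves here only to show that the effects assumed below (0.59 to 0.76) are of the size the trial was planned around.

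**Inputs from the documents.**
- Cut at 50% and odds ratio with two-sided 95% interval: SAP 11.4.2.2.
- Arm sizes: "unbalanced allocation of patients to placebo (n = 20) and overall FDY-5301 treatment groups (n = 60") in SAP section 9, and "randomized in a 1:1:1:1 ratio" in SAP section 7. This gives 20 versus 60 pooled and 20 versus 20 per dose in the evaluable set.
- Up to 160 randomised (Protocol 5.1), and analysis in the intent-to-treat population, repeated per protocol (SAP 11.4). At most this gives 40 versus 120 pooled and 40 versus 40 per dose.

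**Assumed, because not stated.** Placebo and active resolution of 50/75, 60/80 or 70/90%; percentage resolution normal with equal SD, shifted between arms. "Power" below means the chance that a two-sided 95% interval excludes no difference. It is a yardstick for precision.

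**Step 1, standardised shift.** d = Φ⁻¹(active rate) − Φ⁻¹(placebo rate).
- 50/75: 0.674 − 0 = 0.674
- 60/80: 0.842 − 0.253 = 0.588
- 70/90: 1.282 − 0.524 = 0.757

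**Step 2, continuous comparison.** Noncentral t with λ = d·√(n₁n₂/(n₁+n₂)). The root is √15 = 3.873 at 20 versus 60 and √30 = 5.477 at 40 versus 120. For 50/75 at 20 versus 60, λ = 0.674 × 3.873 = 2.61.

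**Step 3, binary comparison.** Exact enumeration of all tables, counting those where the Wald 95% interval for the odds ratio excludes 1 (0.5 added only when a cell is empty). A large-sample check for 50/75 at 20 versus 60: ln 3 = 1.099; SE = √(1/10 + 1/10 + 1/45 + 1/15) = 0.537; ratio 2.04. Then Φ(2.04 − 1.96) = 53%, against 55% by enumeration.

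| Placebo/active resolved | Pooled n | Binary | Continuous | Gap (points) |
|---|---|---|---|---|
| 50/75% | 20 v 60 | 54.7% | 73.2% | 18.5 |
| 60/80% | 20 v 60 | 42.2% | 61.4% | 19.2 |
| 70/90% | 20 v 60 | 53.7% | 82.5% | 28.8 |
| 50/75% | 40 v 120 | 83.0% | 95.7% | 12.6 |
| 60/80% | 40 v 120 | 70.2% | 89.3% | 19.1 |
| 70/90% | 40 v 120 | 83.6% | 98.5% | 14.9 |

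Gaps are taken before rounding. As precision, for 50/75 at 20 versus 60, (2.04/2.61)² = 0.61: the odds ratio works roughly as if about 61% of the patients had been measured.

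**Step 4, wider inputs at 20 versus 60.** With d from 0.4 to 1.2 and placebo resolution from 20 to 80%, the loss runs from about 3 points (d = 1.2, low placebo rate) to about 40 (d = 0.9 with 80% placebo resolution: 93% against 53%). At d = 0.733, the effect with 80% continuous power, it is 19 to 23 points for placebo rates of 30 to 60%.

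**Step 5, one dose against placebo, 20 versus 20, 50/75.** λ = 0.674 × √10 = 2.13. The unadjusted odds ratio gives 34%. An unadjusted t test gives 55%. With Dunnett (three doses, 76 df, critical value about 2.40) it is 40%. Compared with the unadjusted odds ratio, the gain is therefore about 6 points once Dunnett is applied.

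**Step 6, ceiling.** Capping resolution at 100% (assumed SD 30 or 40 points) and using Mann-Whitney at 20 versus 60, simulation gives about 71–72%, 57–59% and 76–79% in the three scenarios. Some 15 to 25 points of gain remain.

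**The case against.** The strongest reply is that nothing here is wrong. The protocol defines the outcome as a proportion analysed by odds ratios, and the SAP follows it and adds confidence intervals. The outcome is exploratory, and no test or power is planned for it. All of that stands, so this is an improvement and not the correction of an error.

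Several stronger readings are tempting, and the documents do not support them.

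- A reader might infer a fixed loss of some 20 points caused by having 20 placebo patients. The placebo rate and effect are not given, so no single figure follows. The 20 versus 60 split is also the set left after the assumed 50% drop-out. ST resolution needs only a 4-hour ECG and is analysed by intent to treat, so the number available lies between 80 and 160 if enrolment reaches its ceiling. At that ceiling the gap narrows to 13–19 points.
- A reader might call this the weakest efficacy comparison. Persistent arrhythmia (SAP 11.4.2.3) is also binary, and it is assessed later, after more time for attrition.
- A reader might point to entry at 0.1 mV and argue that small reading differences flip the category. Protocol 6.1 does allow 0.1 mV in some leads, but Protocol 5.1 and 5.5.1 ask for at least 2 mm in two contiguous leads. Those passages need reconciling before anything is built on the lower figure. The SAP also uses the lead with the greatest elevation.
- A reader might expect dose-level odds ratios to fail often on empty cells. At 70/90% an empty cell occurs in 12% of tables at 20 versus 20, but in only 1.5% at 40 versus 40. The SAP gives no rule for that case, but it is a minor matter.

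**Conclusion.** The point holds as a cheap improvement. The percentage is evaluated and then discarded, and the comparison is less precise as a result. In the three scenarios the pooled loss is about 13 to 29 points of power across the plausible range of patient numbers, and about 3 to 40 points over wider inputs at 20 versus 60. At dose level with Dunnett the gain is small, about 6 points in the one case worked. These figures rest on an assumed placebo rate and effect, a normal percentage with equal SD, and a pure shift; a ceiling at full resolution trims them. The planned odds-ratio analysis remains valid.

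**What to change.** Keep the proportion and the odds ratios in SAP 11.4.2.2 as they are. Add a supportive comparison, fixed before unblinding, of percentage ST resolution at 4 hours on the lead that was worst at baseline:

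- overall FDY-5301 against placebo by Mann-Whitney test, with a Hodges-Lehmann difference and 95% confidence interval. The rank method is chosen in advance because of the ceiling, so no data-driven choice of test is needed;
- each dose against placebo by ANOVA with Dunnett, as for the other continuous outcomes.

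ANCOVA of 4-hour ST elevation on baseline ST elevation is an acceptable alternative if it is the one fixed before unblinding. Its gain was not computed here, because it depends on a baseline correlation that the documents do not give.

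The cost is a paragraph of SAP text and one additional table. No new visit or measurement is needed. The downside is one more nominal exploratory result, which should be labelled supportive.
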